5.4. Analysis of safety and reactogenicity

5.4.1. Analysis of safety and reactogenicity planned in the protocol

The primary analysis will be based on the TVC. If more than 5% of enrolled subjects are excluded from the ATP cohort for analysis of safety, then a second analysis based on this ATP cohort will be performed to complement the TVC analysis. All analyses will be descriptive.

- The percentage of subjects with at least one local symptom (solicited or unsolicited), with at least one general symptom (solicited or unsolicited) and with any symptom (solicited or unsolicited) during the 4-day (Day 0-Day 3) solicited follow-up period will be tabulated with exact 95% CI [Clopper, 1934]. The same calculations will be done for symptoms (solicited or unsolicited) rated as grade 3 in intensity, for symptoms (solicited or unsolicited) leading to medical advice and for symptoms (solicited or unsolicited) assessed as causally related to vaccination.
- The incidence of local AEs (solicited and unsolicited) will be calculated at each injection site as well as overall (all sites considered) for each group.
- The percentage of subjects reporting each individual solicited local and general symptom during the 4-day (Day 0-Day 3) solicited follow-up period will be tabulated after the vaccine dose, with exact 95% CI [Clopper, 1934]. The same calculations will be done for each individual solicited symptom rated as grade 3 in intensity and for each individual solicited symptom assessed as causally related to vaccination.
- All computations mentioned above will be done for Grade ≥ 2 (solicited symptoms only) and grade 3 symptoms, for symptoms considered related to vaccination (general symptoms only), for grade 3 symptoms considered related to vaccination (general symptoms only) and for symptoms that resulted in a medically-attended visit.
- Occurrence of fever and related fever will be reported per 0.5°C cumulative temperature increments as well as the occurrence of grade 3 fever ($> 39.0^{\circ}\text{C}$ axillary temperature) with causal relationship to vaccination.

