- The verbatim reports of unsolicited AEs will be reviewed by a physician and the signs and symptoms will be coded according to MedDRA. Every verbatim term will be matched with the appropriate Preferred Term. The percentage of subjects with unsolicited AEs occurring within 31-day (Day 0- Day 30) follow-up period after any dose with its exact 95% CI [Clopper, 1934] will be tabulated by group, and by preferred term. Similar tabulation will be done for unsolicited AEs rated as grade 3, for unsolicited AEs with causal relationship to vaccination and AEs/SAEs leading to withdrawal from the study.
- The percentage of subjects who receive concomitant medication and antipyretic medication during the 4-day (Day 0- Day 3) follow-up period and during the entire study period will be tabulated (with exact 95% CI [Clopper, 1934]) after the booster dose.
- Any large injection site reaction (defined as any local swelling with diameter > 50 mm and/or any noticeable diffuse injection site swelling (diameter not measurable) and/or any noticeable increased circumference of the injected limb) reported within 4 days (Day 0-Day 3) following the booster dose will be described in detail.
- Subjects who experience at least one SAE from booster vaccination up to study end will be described in detail.
- Subjects who report at least one SAE after the end of primary study 201330 [DTPA (BOOSTRIX)-048 PRI] and before 201334 [DTPA (BOOSTRIX)-049 BST: 048] study will be described in detail.
- Withdrawal due to AEs and SAEs following vaccinations will be described in detail.
- For the subjects who withdraw from the study after Visit 1 (after completion of ASQ-3 questionnaire but have not received booster vaccination), the analysis will be performed on the Total enrolled cohort.
- Neurodevelopmental status of the subjects will be assessed depending on the ASQ-3 score. The proportion of subjects in the black zone for any domain, for gross motor skills, fine motor skills, communication, problem solving skills and personal-social skills will be tabulated. The proportion of infants referred for formal neurodevelopmental evaluation using BSID-III and those with at least one indicators of neurodevelopmental impairment using BSID-III will also be tabulated.

Handling of missing data:

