- For a given subject and the analysis of solicited AEs, four days post-vaccination (Day 0-Day 3), missing or non-evaluable measurements will not be replaced. Therefore, the analysis of the solicited AEs based on the TVC will include only vaccinated subjects and doses with documented safety data (i.e., symptom screen completed).
- For a given subject, missing neurodevelopmental status will not be replaced. Therefore, an analysis will exclude subjects with missing or non-evaluable measurements

- For analysis of unsolicited AEs, such as SAEs or AEs by primary Medical Dictionary for Regulatory Activities (MedDRA) term, and for the analysis of concomitant medications, all vaccinated subjects will be considered. Subjects, whose parent(s)/LAR(s) do not report the event or the concomitant medication, will be considered as subjects without the event or the concomitant medication, respectively.
- For summaries reporting both solicited and unsolicited AEs, all vaccinated subjects will be considered. Subjects, whose parent(s)/LAR(s) do not report the event or the concomitant medication, will be considered as subjects without the event or the concomitant medication, respectively.

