5.4.2.1. Combined Solicited and Unsolicited Adverse Events

For clintrial.gov and EudraCT posting purposes, a summary of combined solicited and unsolicited non-serious adverse events will be produced by System Organ Class and preferred terms and according to occurrence of each event.

A summary of subjects with all combined solicited (regardless of their duration) and unsolicited adverse events will be provided. Solicited adverse events will be coded by MedDRA as per the following codes.

Solicited symptom	Lower level term code	Corresponding Lower level term decode
PA	10022086	Injection site pain
RE	10022098	Redness at injection site
SW	10053425	Swelling at injection site
TE	10016558	Temperature/Fever
FU	10022998	Irritability/Fussiness
DR	10013649	Drowsiness
LO	10003028	Loss of appetite
LS	10060708	Large injection swelling

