10.1.3.10. Counting rules for combining solicited and unsolicited adverse events

For output combining solicited and unsolicited adverse events, all serious adverse events will be considered general events since the administration site flag is not included in the expedited adverse event CRF pages.

Multiple events with the same preferred term which start on the same day are counted as only one occurrence.

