Compliance % = (number of doses with symptom sheet return / number of administered doses) X 100

Template 17 Percentage and nature of <grade 3>symptoms (solicited and unsolicited) reported during the 4-day (Days 0-3) post-vaccination period following each dose and overall (Total vaccinated cohort)

Group	Any symptom					General symptoms					Local symptoms				
	N	n	%	95% CI		N	n	%	95% CI		N	n	%	95% CI	
				LL	UL				LL	UL				LL	UL
dTpa group	335	264	78.8	74.0	83.1	335	134	40.0	34.7	45.5	335	250	74.6	69.6	79.2
Control group	336	279	83.0	78.6	86.9	336	151	44.9	39.5	50.4	336	264	78.6	73.8	82.8

dTpa Group = This group will consist of infants born to mothers belonging to the dTpa Group in study 116945 [DTPA (BOOSTRIX)-047]. All subjects in this group will receive *Infanrix hexa* co-administered with *Prevenar 13* according to the routine national immunisation schedule.

Control Group: This group will consist of infants born to mothers belonging to the Control group in study 116945 [DTPA (BOOSTRIX)-047]. All subjects in this group will receive *Infanrix hexa* co-administered with *Prevenar 13* according to the routine national immunisation schedule.

For each dose and overall/subject:

N= number of subjects with at least 1 administered dose

n(%) = number(percentage) of subjects presenting at least 1 type of symptom whatever the study vaccine administered

For overall/dose:

N= number of administered doses

n(%) = number(percentage) of doses followed by at least 1 type of symptom whatever the study vaccine administered

95% CI = exact 95% confidence interval, LL = Lower Limit, UL = Upper Limit

Template 18 Percentage of solicited local symptoms reported during the 4-day (Day 0-3) post-vaccination period following each dose and overall (Total vaccinated cohort)

Symptom	Type	dTpa group					Control group				
		N	n	%	LL	UL	N	n	%	LL	UL
Pain	All	330	237	71.8	66.6	76.6	329	248	75.4	70.4	79.9
	Grade 3	330	24	7.3	4.7	10.6	329	20	6.1	3.8	9.2
	Medical advice	330	0	0.0	0.0	1.1	329	0	0.0	0.0	1.1
Redness (mm)	All	330	113	34.2	29.1	39.6	329	94	28.6	23.8	33.8
	Grade 3	330	4	1.2	0.3	3.1	329	1	0.3	0.0	1.7
	Medical advice	330	0	0.0	0.0	1.1	329	0	0.0	0.0	1.1
Swelling (mm)	All	330	98	29.7	24.8	34.9	329	90	27.4	22.6	32.5
	Grade 3	330	6	1.8	0.7	3.9	329	5	1.5	0.5	3.5
	Medical advice	330	0	0.0	0.0	1.1	329	0	0.0	0.0	1.1

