Control Group: This group will consist of infants born to mothers belonging to the Control group in study 116945 [DTPA (BOOSTRIX)-047]. All subjects in this group will receive *Infanrix hexa* co-administered with *Prevenar 13* according to the routine national immunisation schedule. For each dose and overall/subject:

N = number of subjects with the administered dose

n* = number of events reported

n/% = number/percentage of subjects reporting the symptom at least once

CONFIDENTIAL

201334 [DTPA (BOOSTRIX) -049 BST: 048]
Statistical Analysis Plan Final

Template 22 Solicited and unsolicited adverse events experienced by subjects classified by MedDRA Primary System Organ Class and Preferred Term within the 31-day (Days 0-30) post-vaccination period - SAE excluded (Total vaccinated cohort)

Primary System Organ Class (CODE)	Preferred Term (CODE)	dTpa Group N =			Control Group N =		
		n*	n	%	n*	n	%
At least 1 symptom							
<each SOC>	<each PT term>						

dTpa Group = This group will consist of infants born to mothers belonging to the dTpa Group in study 116945 [DTPA (BOOSTRIX)-047]. All subjects in this group will receive *Infanrix hexa* co-administered with *Prevenar 13* according to the routine national immunisation schedule.

Control Group: This group will consist of infants born to mothers belonging to the Control group in study 116945 [DTPA (BOOSTRIX)-047]. All subjects in this group will receive *Infanrix hexa* co-administered with *Prevenar 13* according to the routine national immunisation schedule. For each dose and overall/subject:

At least 1 symptom = at least 1 symptom experienced (regardless of the MedDRA Preferred Term)

N = number of subjects with the administered dose

n* = number of events reported

n/% = number/percentage of subjects reporting the symptom at least once

Template 23 Number and percentage of subjects taking a concomitant medication and antipyretic medication during the 4-day (Days 0-3) follow-up period post-vaccination by dose and overall (Total vaccinated cohort)

	dTpa group					Control group				
				95% CI					95% CI	
	N	n	%	LL	UL	N	n	%	LL	UL
Overall/subject										
Any										
Any antipyretic										
Prophylactic antipyretic										

dTpa Group = This group will consist of infants born to mothers belonging to the dTpa Group in study 116945 [DTPA (BOOSTRIX)-047]. All subjects in this group will receive *Infanrix hexa* co-administered with *Prevenar 13* according to the routine national immunisation schedule.

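### SAP 10.1.3.10 counts every SAE as a general event, so a serious injection-site reaction falls in the wrong column of the combined Day 0-3 reactogenicity table

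*SAP*

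**What the plan says.** SAP 10.1.3.10 governs outputs that combine solicited and unsolicited events. Its rule for SAEs is that "all serious adverse events will be considered general events since the administration site flag is not included in the expedited adverse event CRF pages".

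SAP 5.4.1 plans two outputs of that kind, and Protocol 10.8 plans the same two:

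- For the Day 0-3 window: "The percentage of subjects with at least one local symptom (solicited or unsolicited), with at least one general symptom (solicited or unsolicited"), together with an any-symptom rate and grade 3, related and medical-advice versions.
- For local events: "The incidence of local AEs (solicited and unsolicited) will be calculated at each injection site as well as overall".

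The mock-up for the first is Template 17 in SAP section 12, which covers "symptoms (solicited and unsolicited) reported during the 4-day (Days 0-3) post-vaccination period following each dose and overall (Total vaccinated cohort") and has Any, General and Local column blocks with exact 95% intervals.

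On coding, SAP 5.4.1 says of unsolicited AEs: "Every verbatim term will be matched with the appropriate Preferred Term".

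**The concern.** A serious injection-site event is local by nature, yet the rule moves it to the general side of every table that splits the two. The events it misplaces are the most serious local reactions, and those matter most in the low-count local rows (grade 3, medically attended).

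The two vaccines go into opposite sides (Protocol Table 10). Local reactions are therefore the part of the safety data that can be tied to one vaccine, whereas Protocol 8.2.3.2.2 accepts that general AEs may not be attributable to a single vaccine. A related injection-site SAE would also enter related-event rows that SAP 5.4.1 reserves for general symptoms. At stake is the accuracy of a descriptive secondary objective, the reactogenicity of the booster dose. No hypothesis test depends on it.

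**Working it through.** **Are SAEs in these outputs?** Yes. Neither SAP 5.4.1 nor Protocol 10.8 excludes them from the two outputs above. The missing-data rules in SAP 5.4.1 place SAEs among unsolicited events ("For analysis of unsolicited AEs, such as SAEs or AEs by primary Medical Dictionary for Regulatory Activities (MedDRA) term"), and 10.1.3.10 would be pointless if they were absent.

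**Which outputs does the rule reach?**

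| Output | Affected? | Reason |
|---|---|---|
| Template 17, Local and General columns, and versions | Yes | Combined, split local/general |
| Combined local AE incidence, per site and overall | Yes | Combined, local only |
| Template 17, Any column | No | The infant counts either way |
| Template 18, solicited local symptoms | No | Solicited only, from the diary screens |
| Large-swelling description and listing (Template 28) | No | Separate eCRF sheet |
| SAE table and listing (Templates 21, 26) | No | By preferred term, no local/general split |
| Registry summary (SAP 5.4.2.1, Template 22) | No | SAEs excluded |

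For the registry row, SAP 5.4.2.1 states that "a summary of combined solicited and unsolicited non-serious adverse events will be produced by System Organ Class and preferred terms", and the Template 22 title reads "within the 31-day (Days 0-30) post-vaccination period - SAE excluded (Total vaccinated cohort").

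**When does an infant change rows?** The rates count subjects. The infant drops out of Local only if no other local symptom was recorded, or, in a grade 3 or medical-advice version, none that meets that criterion. The infant is added to General only if no other general symptom was recorded.

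**Does the missing flag force the rule?** For the local/general split, no: a preferred term naming the injection or vaccination site marks the event as local. For the per-site rows, largely yes: a preferred term does not say which limb.

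**Size.** The documents give no figure to reproduce for this rule. As a check on the interval method (Clopper-Pearson, SAP 10.1.5.1), the Template 17 placeholder counts give 250/335 = 74.6% [69.6, 79.2] and 134/335 = 40.0% [34.7, 45.5], as printed there.

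Inputs: n = 340 per group, the planned maximum, because the primary safety analysis uses the TVC. The number of serious injection-site events is an assumption, shown for 1 to 3 infants per group.

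- Shift per infant: 1/340 = 0.29 percentage points.
- Exact upper limit: the 0.975 quantile of Beta(x + 1, n − x). For x = 0 this is 1 − 0.025^(1/340) = 1.08%; for x = 1 it is 1.63%.

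| Infants in a rare local row | Rate | Exact 95% CI |
|---|---|---|
| 0/340 | 0.0% | 0.0 to 1.1 |
| 1/340 | 0.3% | 0.0 to 1.6 |
| 2/340 | 0.6% | 0.1 to 2.1 |
| 3/340 | 0.9% | 0.2 to 2.6 |

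For a common row, take the Template 17 placeholders (not results) and one infant with no other symptom of either kind. Moving that infant back changes Local from 250/335 = 74.6% to 251/335 = 74.9%, and General from 134/335 = 40.0% to 133/335 = 39.7%. Any stays at 264/335 = 78.8%.

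**The case against.** The strongest defence is that this is a disclosed, uniform convention tied to what the form collects. It treats both groups alike, all analyses are descriptive, and every SAE after the booster is tabulated by preferred term, listed and described individually. An injection-site SAE would be visible by name.

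Most of that stands, and it limits the importance of the point. It does not make the classification right: a reader of Template 17 would take the Local column to be complete.

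Three stronger readings are tempting, and the documents do not support them.

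- *Serious local reactions disappear from the local rates altogether.* They do not. Template 18 is built from the diary, and an infant with diary-recorded pain, redness or swelling stays in the overall Local column. Protocol 8.2.3.5 asks about medical attention, hospitalisation included, for each solicited symptom, so such an infant can also stay in the medical-advice row. Large swelling has its own sheet and listing.
- *The same reaction will be counted as both local and general.* This is possible but not established. The SAP does not say how a reaction recorded both on the diary card and on the expedited form is handled.
- *The shift is larger because only 204 to 272 infants per group are evaluable.* Those figures (Protocol 10.3) describe precision for seroprotection and booster response after losses that include protocol violations. They are not the TVC.

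It is also fair to say that coding cannot recover the limb, so the per-site rows can be only partly repaired.

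**Conclusion.** The point holds within narrow limits. SAP 10.1.3.10 misclassifies a serious injection-site event as general in the combined Day 0-3 table and its versions, and leaves it out of the combined local AE incidence, when the infant has no other qualifying local symptom.

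The consequence is small: about 0.29 percentage points per infant at 340 per group, and for a rare local row an upper limit of 1.1% where 1.6% is correct. With fewer than 340 vaccinated in a group the shift is slightly larger. The conclusion rests on two assumptions: that at least one such event occurs, which is expected to be rare and which the documents neither predict nor rule out, and that its coded term names the injection or vaccination site. No endpoint definition or conclusion of the study turns on it. It is a worthwhile tidy-up, not a serious flaw.

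**What to change.** Replace the SAE sentence in SAP 10.1.3.10 with wording such as:

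> In outputs combining solicited and unsolicited adverse events, an SAE whose MedDRA preferred term is an injection-site or vaccination-site term is counted as local in the overall local row. It is counted in a per-site row only if the SAE report identifies the limb; otherwise the per-site table carries a footnote giving the number of local SAEs not assigned to a site. All other SAEs are counted as general. An SAE that duplicates a diary-recorded local reaction is not also counted as general.

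The cost is one SAP sentence and a brief manual check of the few SAEs in the window; no new data are collected. The drawback is some reliance on how the verbatim term was coded: a local event recorded under a term that does not name the site would still be counted as general unless the check catches it.

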10.1.3.11. Counting rules for occurrences of solicited adverse events

When the occurrences of solicited adverse events are summarized, each event recorded as having occurred during a specific period will be counted as only one occurrence regardless of the number of days on which it occurs. Also, in the case of co-administered study vaccines, an injection site reaction recorded for a subject following multiple vaccines will be counted as only one occurrence.

10.1.4. Display of decimals

The following decimal description from the decision rules will be used for the demography, immunogenicity and safety/reactogenicity.

Display Table	Parameters	Number of decimal digits
Demographic characteristics	Mean, median age	1
Demographic characteristics	SD (age)	1
Immunogenicity	GMT/GMC	3 for anti-D, anti-T and anti-PRP 2 for Strepto antigens 1 for anti-PT, anti-FHA and anti-PRN, anti-HBs, anti-Polio 1, anti-Polio 2 and anti-Polio 3
Reactogenicity	Mean, Min, Q1, Median, Q3, Max for duration	1
All summaries	% of count, including LL & UL of CI	1

10.1.5. Statistical methodology**10.1.5.1. Exact confidence intervals around proportions**

The exact confidence intervals around within-group proportions are derived using the method of Clopper and Pearson [[Clopper, 1934](#)].

10.2. TFL ToC

The TFL ToC can be found in eTMF folder section 11.1.1.

12. ANNEX 3: STUDY SPECIFIC MOCK TFL

The following drafted study specific mocks will be used.

The data display, title and footnote are for illustration purpose and will be adapted to the study specificity as indicated in the TFL TOC.

These templates were copied from recent studies. Note that there may be few changes between the study specific SAP mock TFL and the final TFLs as editorial/minor changes do not require a SAP amendment.

Template 1 Number of subjects enrolled by center (Total vaccinated cohort)

Center	dTpa Group		Control group	
	n	N	n	%
PPD				
PPD				
PPD				
PPD				
PPD				
PPD				
PPD				
PPD				
PPD				
PPD				
PPD				
PPD				
All				

dTpa Group = This group will consist of infants born to mothers belonging to the dTpa Group in study 116945 [DTPA (BOOSTRIX)-047]. All subjects in this group will receive *Infanrix hexa* co-administered with *Prevenar 13* according to the routine national immunisation schedule.

Control Group: This group will consist of infants born to mothers belonging to the Control group in study 116945 [DTPA (BOOSTRIX)-047]. All subjects in this group will receive *Infanrix hexa* co-administered with *Prevenar 13* according to the routine national immunisation schedule.

n = number of subjects included in each group or in total for a given center or for all centers

All = sum of all subjects in each group or in total (sum of all groups)

% = $n/All \times 100$

CONFIDENTIAL

201334 [DTPA (BOOSTRIX) -049 BST: 048]
Statistical Analysis Plan Final

Template 2 Number of subjects enrolled by country (Total vaccinated cohort)

Country	dTpa Group	Control group	Total	
	n	N	n	%
Australia				
Belgium				
Canada				
Czechia				
Finland				
Italy				
Spain				
All				

dTpa Group = This group will consist of infants born to mothers belonging to the dTpa Group in study 116945 [DTPA (BOOSTRIX)-047]. All subjects in this group will receive *Infanrix hexa* co-administered with *Prevenar 13* according to the routine national immunisation schedule.

Control Group: This group will consist of infants born to mothers belonging to the Control group in study 116945 [DTPA (BOOSTRIX)-047]. All subjects in this group will receive *Infanrix hexa* co-administered with *Prevenar 13* according to the routine national immunisation schedule.

n = number of subjects included in each group or in total for a given country or for all countries

All = sum of all subjects in each group or in total (sum of all groups)

% = $n/All \times 100$

Template 3 Number of subjects vaccinated, completed and withdrawn with reason for withdrawal (Total vaccinated cohort)

	dTpa Group	Control Group	Total
Number of subjects vaccinated			
Number of subjects completed			
Number of subjects withdrawn			
Reasons for withdrawal:			
Serious Adverse Event			
Non-serious adverse event			
Protocol violation			
Consent withdrawal (not due to an adverse event)			
Migrated/moved from study area			
Lost to follow-up (subjects with incomplete vaccination course)			
Lost to follow-up (subjects with complete vaccination course)			
Others			

dTpa Group = This group will consist of infants born to mothers belonging to the dTpa Group in study 116945 [DTPA (BOOSTRIX)-047]. All subjects in this group will receive *Infanrix hexa* co-administered with *Prevenar 13* according to the routine national immunisation schedule.

Control Group: This group will consist of infants born to mothers belonging to the Control group in study 116945 [DTPA (BOOSTRIX)-047]. All subjects in this group will receive *Infanrix hexa* co-administered with *Prevenar 13* according to the routine national immunisation schedule.

Vaccinated = number of subjects who were vaccinated in the study

Completed = number of subjects who completed last study visit

Withdrawn = number of subjects who did not come for last study visit

Template 4 Number of subjects at each visit and list of withdrawn subjects (Total Vaccinated Cohort)

Group	VISIT	N	Withdrawn Subject numbers	Reason for withdrawal
dTpa Group	VISIT 1	508	no. PP	CONSENT WITHDRAWAL
			no. PP	CONSENT WITHDRAWAL
			no. PPD	CONSENT WITHDRAWAL
			no. PPD	CONSENT WITHDRAWAL
	VISIT 2	504	no. PPD	CONSENT WITHDRAWAL
			no. PPD	CONSENT WITHDRAWAL
			no. PPD	SERIOUS ADVERSE EXPERIENCE
	VISIT 3	501	no. P	MIGRATION FROM STUDY AREA
			no. PP	CONSENT WITHDRAWAL
			no. PP	MIGRATION FROM STUDY AREA
			no. PP	CONSENT WITHDRAWAL
			no. PP	MIGRATION FROM STUDY AREA
			no. PP	MIGRATION FROM STUDY AREA
			no. PPD	CONSENT WITHDRAWAL
Control Group	VISIT 1	257	no. PP	PROTOCOL VIOLATION
			no. PPD	CONSENT WITHDRAWAL
	VISIT 2	255		

CONFIDENTIAL

201334 [DTPA (BOOSTRIX) -049 BST: 048]
Statistical Analysis Plan Final

Group	VISIT	N	Withdrawn Subject numbers	Reason for withdrawal
			no. PPD	CONSENT WITHDRAWAL
	VISIT 3	254		
			no. PP	MIGRATION FROM STUDY AREA
			no. PP	LOST TO FOLLOW-UP
			no. PP	LOST TO FOLLOW-UP
			no. PP	CONSENT WITHDRAWAL
			no. PP	MIGRATION FROM STUDY AREA
			no. PPD	LOST TO FOLLOW-UP
			no. PPD	ADVERSE EXPERIENCE

dTpa Group = This group will consist of infants born to mothers belonging to the dTpa Group in study 116945 [DTPA (BOOSTRIX)-047]. All subjects in this group will receive *Infanrix hexa* co-administered with *Prevenar 13* according to the routine national immunisation schedule.

Control Group: This group will consist of infants born to mothers belonging to the Control group in study 116945 [DTPA (BOOSTRIX)-047]. All subjects in this group will receive *Infanrix hexa* co-administered with *Prevenar 13* according to the routine national immunisation schedule.

N = number of subjects who are still in the study up to the visit

Withdrawn = subject who did not return after the visit

Template 5 Number of subjects enrolled into the study as well as excluded from ATP analyses with reasons for exclusion

Title	Total				dTpa Group			Control Group		
	N	n	s	%	N	n	s	N	n	s
Total enrolled cohort	1200				300			300		
Invalid informed consent or fraud data (code 900)										
Study vaccine dose not administered AT ALL but subject number allocated (code 1030)										
TVC	1200			100	300			300		
Administration of vaccine(s) forbidden in the protocol (code 1040)		2	2			0	0		0	0
Randomisation code broken at the investigator site OR at GSK Safety department (1060)										
Study vaccine dose not administered according to protocol (code 1070)		73	73			23	23		16	16
Vaccine temperature deviation (code 1080)										
Expired vaccine administered (code 1090)		10	11			3	3		1	1
Protocol violation (inclusion/exclusion criteria) (code 2010)		1	1			1	1		0	0
Administration of any medication forbidden by the protocol (code 2040)		1	1			0	0		1	1
Underlying medical condition forbidden by the protocol (code 2050)		1	1			0	0		0	0
Concomitant infection related to the vaccine which may influence immune response (2060)										
Concomitant infection not related to the vaccine which may influence immune response (code 2070)		0	1			0	0		0	1
Noncompliance with vaccination schedule (including wrong and unknown dates) (code 2080)		14	16			6	7		3	4
Noncompliance with blood sampling schedule (including wrong and unknown dates) (code 2090)		12	16			3	5		4	5
Essential serological data missing (code 2100)		87	95			20	22		23	26
Obvious incoherence, abnormal serology evolution or error in data (code 2120)		1	1			0	0		0	0
ATP cohort for analysis of immunogenicity	998			83.2	244			252		

dTpa Group = This group will consist of infants born to mothers belonging to the dTpa Group in study 116945 [DTPA (BOOSTRIX)-047]. All subjects in this group will receive *Infanrix hexa* co-administered with *Prevenar 13* according to the routine national immunisation schedule.

Control Group: This group will consist of infants born to mothers belonging to the Control group in study 116945 [DTPA (BOOSTRIX)-047]. All subjects in this group will receive *Infanrix hexa* co-administered with *Prevenar 13* according to the routine national immunisation schedule.

Note: Subjects may have more than 1 elimination code assigned

n = number of subjects with the elimination code assigned excluding subjects who have been assigned a lower elimination code number

s = number of subjects with the elimination code assigned

% = percentage of subjects in the per protocol set (ATP) relative to the TVC(ES)

CONFIDENTIAL

201334 [DTPA (BOOSTRIX) -049 BST: 048]

Statistical Analysis Plan Final

Template 6 Deviations from specifications for age and intervals between study visits for subjects vaccinated with *Infanrix hexa* (<2> dose schedule - 1 dose/visit) (Total Vaccinated Cohort)

Group		Age	VAC_1-SER_2	
		Protocol	Protocol	Adapted
		DOB to vaccination is 11-18months of age*	from 30 to 48 days	from 21 to 48 days
dTpa Group	N	335	329	329
	n	0	11	8
	%	0.0	3.3	2.4
	range	10 to 15	28 to 74	28 to 74
Control Group	N	336	329	329
	n	0	10	8
	%	0.0	3.0	2.4
	range	10 to 15	29 to 95	29 to 95

Group		Age	VAC:1-VAC:2	VAC:2-SER:2
		Protocol	Protocol	Protocol
		from 6 to 14 weeks and 6 days	from 52 to 78 days	from 21 to 48 days
dTpa Group	N			
	n			
	%			
	range			
Control Group	N			
	n			
	%			
	range			

dTpa Group = This group will consist of infants born to mothers belonging to the dTpa Group in study 116945 [DTPA (BOOSTRIX)-047]. All subjects in this group will receive *Infanrix hexa* co-administered with *Prevenar 13* according to the routine national immunisation schedule.

Control Group: This group will consist of infants born to mothers belonging to the Control group in study 116945 [DTPA (BOOSTRIX)-047]. All subjects in this group will receive *Infanrix hexa* co-administered with *Prevenar 13* according to the routine national immunisation schedule.

N = total number of subjects with available results

n(%) = number(percentage) of subjects with results outside of the interval

range = minimum-maximum for age and intervals

VAC:1 = vaccination at visit 1

VAC:2 = vaccination at visit 2

SER:2 = blood sample collected before the first dose and 1 month after the last dose of the primary vaccination course

2 dose schedule = subjects who received 2 dose of *Infanrix hexa* at 2,4 months of age or 3,5 months of age, co-administered with *Prevenar 13* (according to the routine national immunisation schedule of the country).

* Window from DOB to vaccination is 11-18(+30 days) months of age according to the routine national/ local immunization schedule or as specified in the SPM

Template 7 Summary of demographic characteristics (Total vaccinated cohort)

Characteristics	Parameters or Categories	dTpa Group N =		Control Group N =		Total N =	
		Value or n	%	Value or n	%	Value or n	%
Age (week) at vaccination dose: 1	Mean						
	SD						
	Median						
	Q1						
	Q3						
Gender	Female						
	Male						
Geographic Ancestry	African Heritage / African American						
	American Indian or Alaskan Native						
	Asian - Central / South Asian Heritage						
	Asian - East Asian Heritage						
	Asian - Japanese Heritage						
	Asian - South East Asian Heritage						
	Native Hawaiian or Other Pacific Islander						
	White - Arabic / North African Heritage						
	White - Caucasian / European Heritage						
	Other (Hispanic)						
Dose schedule	2 dose schedule						
	3 dose schedule						
Maternal age group	18-24Y						
	25-34Y						
	35-45Y						
Gestational week of foetus at dose 1	27-32W						
	33-36W						

dTpa Group = This group will consist of infants born to mothers belonging to the dTpa Group in study 116945 [DTPA (BOOSTRIX)-047]. All subjects in this group will receive *Infanrix hexa* co-administered with *Prevenar 13* according to the routine national immunisation schedule.

Control Group: This group will consist of infants born to mothers belonging to the Control group in study 116945 [DTPA (BOOSTRIX)-047]. All subjects in this group will receive *Infanrix hexa* co-administered with *Prevenar 13* according to the routine national immunisation schedule.

N = total number of subjects

n(%) = number(percentage) of subjects in a given category

Value = value of the considered parameter

SD = standard deviation

Q1 = Quartile 1

Q2 = Quartile 3

2 dose schedule = subjects who received 2 dose of *Infanrix hexa* at 2,4 months of age or 3,5 months of age, co-administered with *Prevenar 13* (according to the routine national immunisation schedule of the country).

3 dose schedule = subjects who received 3 dose of *Infanrix hexa* at 2,3,4 months of age or 2,4,6 months of age, co-administered with *Prevenar 13*. *Prevenar 13* could be administered as 2-doses or 3-doses primary vaccination schedule (according to the routine national immunisation schedule of the country).

18-24Y = 18-24 years old subjects

25-34Y = 25-34 years old subjects

35-45Y = 35-45 years old subjects

27-32W = 27-32 weeks of gestation of foetus at dose 1

33-36W = 33-36 weeks of gestation of foetus at dose 1

Template 8 Summary of vital signs characteristics (Total Vaccinated Cohort)

		dTpa Group (N = 335)	Control Group (N = 336)	Total (N = 671)
Characteristics	Parameters	Value	Value	Value
Height (cm)	Mean			
	SD			
	Median			
	Q1			
	Q3			
	Unknown			
Weight (kg)	Mean			
	SD			
	Median			
	Q1			
	Q3			
	Unknown			
Head circumference (cm)	Mean			
	SD			
	Median			
	Q1			
	Q3			
	Unknown			
Body mass index in [kg/m ²]	Mean			
	SD			
	Median			
	Q1			
	Q3			
	Unknown			

dTpa Group = This group will consist of infants born to mothers belonging to the dTpa Group in study 116945 [DTPA (BOOSTRIX)-047]. All subjects in this group will receive *Infanrix hexa* co-administered with *Prevenar 13* according to the routine national immunisation schedule.

Control Group: This group will consist of infants born to mothers belonging to the Control group in study 116945 [DTPA (BOOSTRIX)-047]. All subjects in this group will receive *Infanrix hexa* co-administered with *Prevenar 13* according to the routine national immunisation schedule.

N = total number of subjects

Value = value of the considered parameter

SD = standard deviation

Height (cm) = height expressed in centimeters

Weight (kg) = weight expressed in kilograms

Head circumference(cm) = head circumference expressed in centimeters.

Body mass index in [kg/m²] = body mass index expressed in kilograms per meter square

SD = standard deviation

Q1 = Quartile 1

Q2 = Quartile 3

Template 9 Study population (TVC)

Study population (Total vaccinated cohort)		
Number of subjects	dTpa group	Control group
Planned, N	225	225
Randomised, N (Total Vaccinated Cohort)	224	227
Completed, n (%)	224 (100)	227 (100)
Demographics	dTpa group	Control group
N (Total Vaccinated Cohort)	224	227
Females: Males	97:127	115:112
Mean Age, weeks (SD)	8.8 (1.1)	8.8 (1.1)
Median Age, weeks (minimum, maximum)	9 (7, 11)	9 (7, 11)
Most frequent race: Asian - East Asian Heritage, n (%)	224 (100)	226 (99.6)

dTpa Group = This group will consist of infants born to mothers belonging to the dTpa Group in study 116945 [DTPA (BOOSTRIX)-047]. All subjects in this group will receive *Infanrix hexa* co-administered with *Prevenar 13* according to the routine national immunisation schedule.

Control Group: This group will consist of infants born to mothers belonging to the Control group in study 116945 [DTPA (BOOSTRIX)-047]. All subjects in this group will receive *Infanrix hexa* co-administered with *Prevenar 13* according to the routine national immunisation schedule.

N = total number of subjects enrolled in the study

n/% = number/percentage of subjects in a given category

SD = Standard Deviation

Mean Age = age calculated from Date of birth to first study vaccination

Template 10 Seropositivity rates and GMCs for anti-PT, anti-FHA and anti-PRN antibodies before the first dose and 1 month after the last dose of the primary vaccination (ATP cohort for immunogenicity)

Antibody	Group	Timing	N	≥ assay cut-off*				GMC		
				n	%	LL	UL	value	95% CI	
								LL	UL	
Anti-PT	dTpa Group	Pre-Pri								
		Post-Pri								
	Control Group	Pre-Pri								
		Post-Pri								
Anti-FHA	dTpa Group	Pre-Pri								
		Post-Pri								
	Control Group	Pre-Pri								
		Post-Pri								
Anti-PRN	dTpa Group	Pre-Pri								
		Post-Pri								
	Control Group	Pre-Pri								
		Post-Pri								

dTpa Group = This group will consist of infants born to mothers belonging to the dTpa Group in study 116945 [DTPA (BOOSTRIX)-047]. All subjects in this group will receive *Infanrix hexa* co-administered with *Prevenar 13* according to the routine national immunisation schedule.

Control Group: This group will consist of infants born to mothers belonging to the Control group in study 116945 [DTPA (BOOSTRIX)-047]. All subjects in this group will receive *Infanrix hexa* co-administered with *Prevenar 13* according to the routine national immunisation schedule.

*Assay cut-off is 2.693 IU/mL for anti- PT, 2.046 IU/mL for anti-FHA and 2.187 IU/mL for anti-PRN

GMC = geometric mean antibody concentration calculated on all subjects

N = number of subjects with available results

n(%)=number(percentage) of subjects with antibody concentrations above the specified cut-off

95% CI = exact 95% confidence interval; LL = Lower Limit, UL = Upper Limit

Pre-Pri = blood sample to be collected before the first dose of the primary vaccination course

